Cover Page: ECT Current Amplitude and medial temporal lobe engagement (MH111826)

ClinicalTrials.gov Identifier: NCT02999269

Document Date: November 24, 2021

Study Protocol and Statistical Analysis

Study Protocol

All subjects started the ECT series with right unilateral (d'Elia) electrode placement (28). Subjects were randomized and blinded to 600, 700, and 800 mA prior to the first ECT treatment. Subject randomization was completed with a random number generator prior to study initiation with a 1:1:1 ratio for each study arm. As determined by our preliminary data, 500 mA pulse amplitudes compromised efficacy. Subjects received clinical, neuropsychological, and imaging assessments pre- (V1), mid- (after the sixth ECT treatment, V2) and post-ECT (within one week of finishing the ECT series, V3). If subjects were non-responsive to the assigned pulse amplitude (< 25% reduction in from baseline HDRS₂₄ at the second visit), subjects then received bitemporal (BT) electrode placement (800 mA, 1.0 milliseconds (ms) pulse width) for the remainder of the ECT series (29).

Subjects received ultrabrief pulse width (0.3 ms) until a planned interim data analysis (n = 47) to ensure that the experimental arms were equipoise with the active comparator. The analysis demonstrated a trend towards the lower efficacy of the 600 mA arm. We subsequently increased the pulse width from ultrabrief (0.3 ms) to brief (1.0 ms) all treatment arms for the remainder of the study (n = 15). The rationale for the increased pulse width, as approved by the National Institutes of Health (NIH) and the study Data Safety Monitoring Board (DSMB), was to improve the efficacy of the lower amplitude arm. The strength-duration curve established that lower pulse amplitudes required longer pulse widths to elicit neuronal activation potential (30, 31). Thus, we reasoned that the increased pulse width may improve the neuronal activation potential and the antidepressant efficacy of the 600 mA arm.

The first ECT session determined individual seizure thresholds with subsequent treatments provided at six times the seizure threshold with similar adjustments to pulse train duration and frequency across all amplitude arms (32). Further adjustments to charge were permitted to ensure adequate seizure morphology and duration based on clinical judgment. Motor, electroencephalographic, and heart rate parameters were recorded for each treatment. The treating anesthesiologist determined the appropriate dose of methohexitol, a general anesthetic, and succinylcholine, a depolarizing neuromuscular blocker.

Statistical Analyses

Clinical and demographic variables were assessed with chi-square or one-way analysis of variance. For the primary outcomes (change in HDRS₂₄ and HVLT-R retention raw score), we performed a full longitudinal model with an unstructured repeated measures covariance matrix on subjects who completed the study in the assigned treatment arm. Missing values for the depression and cognitive variables (14% of values) were imputed using regression multiple imputation with five iterations (33). We completed imputation for seven subjects that did not complete the final post-ECT assessment and for sparse missing cognitive values. When a subject had all their values imputed for a variable, then that subject was removed from the analysis of that variable. In addition, we performed a separate analysis with subjects receiving bitemporal electrode placement between V2 and V3. For depression outcomes, the dependent variable was HDRS at each visit and the independent variables included progress (time within the ECT series: pre-, mid-, and post-ECT), amplitude, age, sex, pulse width and the following interactions: progress/amplitude, progress/sex, and progress/pulse width. For primary cognitive outcomes, the dependent variable was HVLT-R retention scores at each visit with the same model plus the Test of Premorbid Functioning Standard Scores as an additional covariate. In addition to our primary cognitive outcome, we assessed secondary outcomes for the additional cognitive measures using the same cognitive statistical model. Follow-up contrasts included the following: 1) longitudinal changes within each amplitude (e.g., HDRS₂₄ differences in 600 mA subjects between V1 and V2); 2) amplitude contrasts during the mid- and post-ECT assessments (e.g., HDRS₂₄ differences 600 and 700 mA at V2); 3) sex differences; and 4) pulse width differences. The amplitude contrasts were averaged for sex and pulse width with Tukey's method for multiple pairwise comparisons.

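### On its natural reading the primary model leaves out subjects switched for HDRS non-response at V2, so even the pre-switch V2 contrasts do not compare the randomised groups

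*Combined protocol and SAP*

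**What the plan says.** The Study Protocol section sets a switch rule at V2. The trigger is "If subjects were non-responsive to the assigned pulse amplitude (< 25% reduction in from baseline" HDRS-24 at that visit, and the consequence is that "subjects then received bitemporal (BT) electrode placement (800 mA, 1.0 milliseconds (ms) pulse width) for the remainder of the ECT series". It also reports, from the interim look at 47 subjects, that "The analysis demonstrated a trend towards the lower efficacy of the 600 mA arm".

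The Statistical Analyses section names two primary outcomes, change in HDRS-24 and HVLT-R retention. Both are analysed with a "full longitudinal model with an unstructured repeated measures covariance matrix on subjects who completed the study in the assigned treatment arm". On missing data it says: "We completed imputation for seven subjects that did not complete the final post-ECT assessment and for sparse missing cognitive values". On switched subjects it says: "we performed a separate analysis with subjects receiving bitemporal electrode placement between V2 and V3". The follow-up contrasts taken from the model include "longitudinal changes within each amplitude", with V1 to V2 as the example, and "amplitude contrasts during the mid- and post-ECT assessments".

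**The concern.** A subject switched at V2 did not finish in the assigned arm. The primary set is then the subjects with at least 25% HDRS-24 improvement at V2, and that improvement is itself a primary outcome measured after randomisation. Randomisation balances the arms as allocated, not the early responders within each arm.

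The error is clearest at V2. No subject has switched when V2 is measured, so every V2 value is valid data on the assigned amplitude. Dropping the non-responders truncates the outcome being compared. The arm with more non-responders loses more of its poor results, so with equal SDs a true difference shrinks. Covariates and an unstructured covariance cannot repair this, because the excluded rows never enter the model. The trial's own question is whether a lower amplitude costs efficacy, and this analysis would tend to hide such a cost. V3 contrasts carry the same selection. HVLT-R contrasts use the same selected set, with a direction that cannot be determined from the documents.

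**Working it through.** **No design figure to reproduce.** The documents state no effect size, SD, correlation or number switched. The available counts are 47 before and 15 after the pulse-width change: 47 + 15 = 62, about 21 per arm at 1:1:1 if 62 is the randomised total. Everything below illustrates direction and scale under stated assumptions.

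**Selection at V2 in closed form.** Less than 25% reduction means V2 > 0.75·V1. Let D = V2 − 0.75·V1; subjects with D > 0 are dropped. Take V1 and V2 as bivariate normal. Assumed: V1 mean 34, SD 6; V2 SD 9 in both arms; correlation 0.5.

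- Var(D) = 9² + 0.75²·6² − 2·0.75·0.5·9·6 = 81 + 20.25 − 40.5 = 60.75, so SD(D) = 7.794.
- Cov(V2, D) = 81 − 0.75·27 = 60.75. Cov(V1, D) = 27 − 0.75·36 = 0, so the kept subjects' baseline mean stays at 34 and scores and change give the same answer here.
- With a = −(mean V2 − 25.5)/7.794 and λ = φ(a)/Φ(a), the kept V2 mean is (true mean) − (60.75/7.794)·λ = (true mean) − 7.794·λ.

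| True V2 mean | a | Switched | λ | Kept V2 mean | True V1–V2 fall | Fall in kept set |
|---|---|---|---|---|---|---|
| 26 | −0.064 | 53% | 0.839 | 19.46 | 8 | 14.5 |
| 22 | 0.449 | 33% | 0.536 | 17.82 | 12 | 16.2 |
| 18 | 0.962 | 17% | 0.302 | 15.65 | 16 | 18.4 |
| 14 | 1.475 | 7% | 0.145 | 12.87 | 20 | 21.1 |

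Adjacent rows differ by a true 4 points. In the kept set the differences are 19.46 − 17.82 = 1.6, 17.82 − 15.65 = 2.2 and 15.65 − 12.87 = 2.8. With V2 SD 7 instead of 9, means of 18 and 14 give 11% and 3% switching and a difference of 3.2. Two arms on the same row show no difference, but the fall in each is overstated.

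**Range.** The same formulas were run over V2 SD 7, 9, 11; correlation 0.3, 0.5, 0.7; 800 mA mean 12 to 24 in steps of 2; and 600 mA deficit 3 to 6 (3 × 3 × 7 × 4 = 252 scenarios, equal SDs). The share of the true V2 difference that remains is:

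| Switching at 600 mA | Scenarios | Share left, scores (median) | Share left, change |
|---|---|---|---|
| 2–25% | 88 | 53–94% (72%) | 59–94% |
| 26–48% | 92 | 30–71% (52%) | 39–65% |
| 52–82% | 72 | 19–57% (38%) | 27–50% |

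A separate simulation that instead drew the percentage reduction as normal (SD 0.20 to 0.30; baseline mean 34, SD 7) left 43–56% of the difference.

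**Unequal SDs.** Hold 800 mA at SD 9, the true difference at 4, and let the 600 mA SD be 5, 6, 11 or 13.

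- Heavy switching (means 26 and 22): scores 5.7, 4.6, −0.2, −1.9; change 3.50, 3.18, 0.34, −1.05.
- Lighter switching (means 18 and 14): scores 4.8, 4.4, 1.4, −0.2; change 4.5, 4.2, 1.6, 0.3.

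Shrinkage is therefore not guaranteed.

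**V3.** Take the 53% v 33% case with V3 SD 9, correlation 0.6 with V2 and 0.5·0.6 = 0.3 with V1. Cov(V3, D) = 0.6·81 − 0.75·0.3·54 = 36.45, so the completer difference is 4 − (36.45/7.794)·(0.839 − 0.536) = 2.6. The no-switch value is 4.0. If bitemporal treatment adds g points, the treatment-policy value is 4 − g·(0.526 − 0.327): 4.0, 3.2, 2.4 or 1.6 for g = 0, 4, 8 or 12. How far completers are from the truth depends on which of these is the target.

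**The specified model.** A simulation fitted the plan's terms with unstructured covariance and Tukey adjustment (21/21/20 subjects, true 600–800 difference 4, 1,500 replicates per scenario). Mean V2 estimates were:

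| Switching at 600 mA | Completers | All randomised |
|---|---|---|
| 52% | 1.8 | 4.1 |
| 33% | 2.2 | 4.1 |
| 17% | 2.8 | 4.0 |
| 12% | 3.2 | 4.0 |

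With a true difference of 0 the two gave −0.1 and 0.0.

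**The case against.** The exclusion is inferred. The plan never says in words that switched subjects' V1 and V2 rows are removed, and completion is not applied literally, because seven subjects without a final assessment are kept by imputation. The imputation account is also incomplete: seven missing V3 visits among 62 subjects and three visits are 7/186 = 3.8%, against 14% of values imputed, with the rest described only as sparse cognitive gaps. This leaves room for doubt, but it does not put switched subjects back. The stated imputation is for absent assessments, not for changed treatment.

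The separate analysis may mean adding bitemporal subjects to everyone else. If so, an all-subject V2 contrast already exists. That would soften the point, but that analysis is still not the primary one.

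V3 is largely an estimand question. After the switch everyone receives the same different treatment, so analysing switched subjects apart is understandable, and no replacement is free of cost. That stands.

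Size and direction in this trial are unknown, and the only sign of unequal arms is an interim trend at 0.3 ms, before the pulse width changed. That also stands. It limits what can be said about the amount of bias, not about whether the analysed groups are the randomised ones.

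**Conclusion.** The concern holds and should be fixed, because it affects the primary set and listed contrasts for both primary outcomes. On the natural reading, V2 and V3 amplitude contrasts from the primary model cannot be read as effects of randomised amplitude, and the within-arm V1–V2 fall is overstated even when the arms are equal.

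If the arms differ in mean response with equal SDs, the V2 HDRS difference is reduced. In the illustrations between about one fifth and nine tenths of it remains, depending mainly on how many subjects switch. Equal arms give no between-arm HDRS bias; strongly unequal SDs can change or reverse the direction. All sizes rest on assumed means, SDs and correlations. The firm part is V2; at V3 the discrepancy depends on an estimand that the plan does not state.

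**What to change.** - Make the primary set all randomised subjects by assigned amplitude, with everyone's V1 and V2 values in the longitudinal model already specified.
- For V3, state which estimand is primary and why, and report both: a treatment-policy contrast using all observed V3 values, and a hypothetical contrast with post-switch V3 set to missing.
- For the hypothetical contrast, include V1 and V2 HDRS and amplitude in the imputation or joint model. Do this for HVLT-R and the other cognitive outcomes too, because the switch depends on HDRS and the listed cognitive model has no HDRS term.
- Report the number switched per arm, and say whether the separate bitemporal analysis covers switched subjects alone or everyone.
- Keep the completer analysis as a sensitivity analysis.

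If switched subjects' V1 and V2 rows were in fact retained, one sentence saying so settles the V2 point; V3 still needs its estimand.

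The cost is SAP wording and a refit on data already collected. The document is written in the past tense, so the reanalysis should be labelled post hoc. In the planned-model simulation the V2 standard error changed by −4% to +7%, and the hypothetical V3 standard error was 0–6% wider than in completers. Tukey power for 4 points was 17–28% with all randomised subjects, against 4–20% in completers, so the fix removes the selection but does not make the trial well powered. These precision figures depend on SDs that the documents do not give. The hypothetical V3 contrast relies on extrapolation, since no on-assignment V3 exists above the switch cutoff; the treatment-policy contrast avoids that but mixes in the bitemporal effect. The authors should declare that trade-off.

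### If the five iterations are five imputed datasets, near-threshold contrasts involving missing outcomes (V3 for HDRS) depend avoidably on the imputation seed

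*Combined protocol and SAP*

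**What the plan says.** All of this is in the Statistical Analyses section. For the primary outcomes (HDRS and HVLT-R retention), "we performed a full longitudinal model with an unstructured repeated measures covariance matrix on subjects who completed the study in the assigned treatment arm". The dependent variable is the score at each visit. Missing depression and cognitive values, put at 14% of values, "were imputed using regression multiple imputation with five iterations".

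On where the gaps lie: "We completed imputation for seven subjects that did not complete the final post-ECT assessment and for sparse missing cognitive values". On subjects with no data for a variable: "When a subject had all their values imputed for a variable, then that subject was removed from the analysis of that variable". Subjects switched after V2 are handled apart: "we performed a separate analysis with subjects receiving bitemporal electrode placement between V2 and V3".

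The follow-up comparisons include "amplitude contrasts during the mid- and post-ECT assessments", with Tukey's adjustment. "The amplitude contrasts were averaged for sex and pulse width".

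The section does not give the number of completed datasets (if that differs from five), the imputation model, the pooling rule, the seed or the estimation method of the longitudinal model.

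**The concern.** Multiple imputation draws random values. With few datasets, the pooled estimate and its standard error both move when the seed changes. A contrast far from the threshold survives this. One close to it can be significant in one run and not in another, on the same data.

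Much of this noise looks avoidable. If the stated model is fitted by ML or REML, it already uses each subject's observed visits under missing at random, with no random draws. Subjects with nothing observed for a variable are removed, so with complete covariates imputing the outcome keeps nobody whom a direct fit would lose. If imputation is preferred, more datasets cost almost nothing.

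At stake is whether a borderline amplitude contrast at V3, on either primary outcome, can be reproduced.

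**Working it through.** **Inputs from the document.** 47 subjects before the pulse-width change and 15 after, so 47 + 15 = 62 if the two phases add; seven absent V3 assessments; three amplitudes; Tukey-adjusted contrasts at V2 and V3; 14% of values missing.

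**Assumed.** Two-sided alpha of 0.05; five iterations = five datasets; an analysed number between 45 and 62. The 62 includes subjects later switched to bitemporal placement, so it is an upper limit for the primary model.

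**1. The plan's own figure.** Seven V3 values are 7/62 = 11.3% of V3 HDRS values and 7/186 = 3.8% of all HDRS values. With 50 subjects they are 7/50 = 14.0% and 7/150 = 4.7%. The 14% covers depression and cognition together and cannot be rebuilt, so it cannot be used to size either primary outcome.

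**2. Missing information for a V3 mean.** With f the share missing and R² the share of V3 variance explained by V1 and V2:

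λ = 1 − 1 / [1 + (f/(1−f))(1−R²)]

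- f = 7/62: f/(1−f) = 7/55 = 0.127, so λ = 0.113 at R² = 0 and 0.060 at R² = 0.5.
- f = 7/50: f/(1−f) = 7/43 = 0.163, so λ = 0.140 and 0.075.

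Simulated three-arm data with seven V3 values missing gave a mean λ for an arm contrast of 0.063-0.125 with 62 subjects and 0.077-0.174 with 50. A scenario with 45 subjects reached 0.21. I therefore use 0.06-0.21.

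**3. Seed error and efficiency with m datasets.** The seed SD of the pooled estimate, in standard errors, is √(λ/m). Relative efficiency is 1/(1 + λ/m).

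- m = 5: √(0.06/5) = 0.11 to √(0.21/5) = 0.20; efficiency 1/1.012 = 0.988 to 1/1.042 = 0.960, a loss of about 1-4%.
- m = 50: √(0.06/50) = 0.03 to √(0.21/50) = 0.06.

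**4. Share of seeds that cross 0.05.** Scale the total variance to 1 with infinitely many datasets. Then draw 200,000 seeds with

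- estimate = z0 + N(0, λ/m),
- between-dataset variance B = λ·χ²(m−1)/(m−1),
- total variance T = 1 − λ + (1 + 1/m)B,

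and compute the Tukey p for three arms. The ranges cover λ from 0.06 to 0.21, with both large degrees of freedom and Barnard-Rubin degrees of freedom (55 complete-data df assumed).

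| Contrast with many datasets | Event | m = 5 | m = 50 |
|---|---|---|---|
| p = 0.03 | non-significant | 7-34% | at most about 1% |
| p = 0.04 | non-significant | 27-47% | 1-16% |
| p = 0.06 | significant | 22-36% | 2-17% |
| z = 3 | p above 0.05 | 0-11% | not tabulated |

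**5. Cross-check with imputed data.** A separate simulation imputed V3 by regression and pooled by Rubin's rules, over 400 seeds per setting. With five datasets, a contrast at p = 0.04 stayed below 0.05 in 56-78% of seeds, and one at 0.06 fell below in 24-35%. For a contrast centred on p = 0.05, the 95% seed range ran from 0.029-0.096 (50 subjects, λ 0.054) to 0.015-0.187 (45 subjects, λ 0.21). With 50 datasets these ranges were 0.042-0.060 and 0.035-0.075.

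**6. Which contrasts.** The only HDRS gaps described are at V3, so HDRS amplitude contrasts at V2 are essentially unaffected. The visits of the missing cognitive values are not stated.

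**The case against.** The strongest reply is that the harm is conditional at each step: the meaning of the phrase, the analysed number, alpha and a contrast near the threshold. This stands. If the phrase means cycles of the algorithm, the number of datasets is unstated and none of the percentages above applies. The seven absences may also not all fall in the primary model's set, which is described as subjects who completed the study. The range for missing information is therefore an assumption.

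A second reply is that imputation and direct likelihood are both valid under missing at random, so preferring one is taste. This also largely stands. Imputation may draw on auxiliary variables or fill a missing premorbid score, which a direct fit would not do. It does not defend stopping at five datasets, because adding more keeps every benefit of imputation.

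Four stronger readings are tempting, and the document does not support them:

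- **That five datasets bias the results or inflate type I error.** Properly pooled, the variance includes the imputation noise; what suffers is reproducibility.
- **That imputing was wrong and the direct fit should replace it.** The estimation method, the completeness of the covariates and the imputation model are not stated.
- **That a particular finding rests on the seed.** The document reports no p-values.
- **That clear contrasts are always safe.** At the upper end of the range, a z = 3 contrast still exceeds 0.05 in about 11% of seeds.

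**Conclusion.** The concern holds as a minor, conditional one about reproducibility. If five datasets were used, a V3 amplitude contrast with a many-dataset Tukey p between about 0.03 and 0.06 has an appreciable chance of landing on the other side of 0.05 through the seed alone: about 7-34% at 0.03, 27-47% at 0.04 and 22-36% at 0.06. Fifty datasets greatly reduce this but do not abolish it.

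The size rests on missing information of 0.06-0.21, alpha of 0.05 and the seven V3 absences. HVLT-R could not be sized separately. Whether any actual result is affected is unknown.

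**What to change.** **Governing analysis.** Keep the stated imputation analysis and rerun it in the same subjects with at least 50 datasets and a fixed, reported seed. The imputation model should include amplitude by visit and pulse width. Pool by Rubin's rules.

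**Sensitivity analysis, labelled post hoc.** Fit the same model to the observed HDRS and HVLT-R values of the same subjects by REML with Kenward-Roger degrees of freedom. Keep subjects switched to bitemporal placement in their separate analysis. If the two disagree, the imputation result governs and the disagreement is reported.

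**Reporting.** State how many datasets the five iterations were, the denominator of the 14%, and the missing counts by variable and visit. If the phrase meant algorithm cycles, stating the number of datasets is all that this point asks.

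**Cost.** A small re-analysis with no new data. It is post hoc, because the analysis is described as already done. The direct fit also gives up any auxiliary information or missing-covariate handling in the imputation, which is why it should not replace the governing analysis.

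### The primary memory comparison leaves out subjects switched to bitemporal placement for non-response, and no clearly specified analysis gives V3 memory by starting amplitude

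*Combined protocol and SAP*

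**What the plan says.** The Study Protocol section randomises subjects 1:1:1 to 600, 700 or 800 mA with right unilateral placement and assesses them at V1, V2 (after the sixth treatment) and V3 (end of series). Subjects count as non-responsive to the assigned amplitude if they show "< 25% reduction in from baseline HDRS₂₄ at the second visit". In that case "subjects then received bitemporal (BT) electrode placement (800 mA, 1.0 milliseconds (ms) pulse width) for the remainder of the ECT series", whichever arm they began in.

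The Statistical Analyses section fits the model for both primary outcomes, HDRS-24 and HVLT-R retention, "on subjects who completed the study in the assigned treatment arm". For memory, "the dependent variable was HVLT-R retention scores at each visit with the same model plus the Test of Premorbid Functioning Standard Scores" as a further covariate. The follow-up contrasts include "amplitude contrasts during the mid- and post-ECT assessments".

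For switched subjects the section says that "we performed a separate analysis with subjects receiving bitemporal electrode placement between V2 and V3". It does not say which model was used, who was compared with whom, or whether randomised amplitude was a factor. Imputation is described for seven subjects without the final assessment and for sparse missing cognitive values; switched subjects are not mentioned there.

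On efficacy by arm, the Study Protocol section reports of the interim at n = 47 that "The analysis demonstrated a trend towards the lower efficacy of the 600 mA arm". Pulse width was then lengthened in all arms for the remaining 15 subjects.

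**The concern.** The switch rule depends on the depression score at V2, which the assigned amplitude can itself influence. Restricting the primary analysis to subjects who stayed on the assigned settings therefore selects on a consequence of randomisation. For memory there is a second effect: whatever happens to HVLT-R retention after the switch, for better or worse, is absent from the primary V3 contrast between amplitudes.

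Two questions can be asked of V3 memory. One is how memory fares on a given amplitude while that amplitude is maintained. The other is how memory fares when treatment starts at that amplitude and follows the protocol, switch included. The primary model is aimed at the first, though among responders only. Nothing that is clearly specified answers the second. If one arm switches more subjects than another and switchers end with different memory from stayers, the two answers differ, and a reader weighing antidepressant effect against memory would see only one of them.

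The restriction also reaches V2. Read literally, it removes switched subjects' V1 and V2 scores as well, although those were taken before any bitemporal treatment.

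**Working it through.** The documents state no switch rate, HVLT-R standard deviation, effect size or power for this comparison, so there is no planned figure to reproduce. The check is an identity with assumed inputs.

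**Inputs from the documents**
- Counts: 47 before and 15 after the pulse-width change, so 47 + 15 = 62. At 1:1:1 this is 62 / 3 ≈ 20.7 per arm. The text does not say whether these are randomised or analysed subjects.
- Subjects counted before the change: 47 / 62 ≈ 76%.

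**Assumed inputs**
- p = share of an arm switched after V2.
- d = mean V3 retention of switchers minus that of stayers, in SD units and taken as the same in each arm. It combines the effect of the switch with any difference that already existed between non-responders and responders.

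**Identity**

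All-randomised arm mean = (1 − p) × stayer mean + p × (stayer mean + d) = stayer mean + p × d.

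Shift in the 600-minus-800 mA contrast when switchers are put back = (p600 − p800) × d.

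A negative shift means 600 mA does worse on memory than the stayer analysis shows. A simulation with 400,000 subjects per arm agreed: with 50%/20% switching and d = −1.0, a stayer difference of 0.298 SD became −0.003 SD, against 0.30 and 0.30 + 0.3 × (−1.0) = 0.00 from the formula.

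**Results (SD units)**

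| p600 / p800 | d = −0.5 | d = 0 | d = +0.5 |
|---|---|---|---|
| 20% / 20% | 0 | 0 | 0 |
| 40% / 20% | −0.10 | 0 | +0.10 |
| 50% / 20% | −0.15 | 0 | +0.15 |

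For example, (0.4 − 0.2) × (−0.5) = −0.10 and (0.5 − 0.2) × 0.5 = +0.15.

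**Splitting d.** Suppose the switch itself lowers retention by 0.5 SD and switching is 50%/20%. The shift is then 0.3 × (−0.5 + selection):
- selection −0.3: −0.24
- selection 0: −0.15
- selection +0.3: −0.06
- selection +0.6: +0.03

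So even a harmful switch does not fix the sign.

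**Precision.** Unadjusted and cross-sectional, the SE of a two-arm contrast at 20.67 per arm is √(1/20.67 + 1/20.67) ≈ 0.31 SD. Removing 50% and 20% leaves about 10.3 and 16.5, and √(1/10.3 + 1/16.5) ≈ 0.40 SD.

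**The case against.** **The target may be amplitude itself.** The study's title concerns current amplitude, and a contrast on assigned settings is a legitimate aim. HVLT-R is called a primary cognitive outcome, not a safety endpoint. This stands as a reason to keep the existing model. It does not justify having that model alone: the aim is not stated, and dropping everyone who failed to respond is not a neutral way of reaching it.

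**The separate analysis may already do the job.** Its wording can mean switched subjects alone, or a second run of the amplitude model that includes them. On the second reading it comes close to what is asked for here. This stands in part. A reader might infer that post-switch memory is counted against no randomised arm anywhere. That is clear for the primary model, but the separate analysis is described too thinly to say so of the whole plan.

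**The direction is not shown.** A reader might infer that 600 mA must look safer for memory than it is. That needs more switching at 600 mA and worse V3 memory among switchers. The documents give no switch counts by arm, no HVLT-R results, and no statement that the bitemporal course harms memory more. The evidence for unequal switching is an interim efficacy trend whose endpoint and timing are not given. It arose before the pulse-width change, which was made to improve that arm. The trend still covers the larger share of subjects and makes unequal switching plausible, but no more than that. This objection stands in full.

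**The shifts are small relative to precision.** The tabulated values of up to 0.15 SD lie below a standard error of about 0.31 SD. That is true. It limits what either analysis can show, but it does not remove the selection.

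**Conclusion.** The point holds as a gap in specification with a conditional bias. The primary HVLT-R amplitude contrasts are conditioned on response at V2, and no clearly specified analysis gives V3 memory by starting amplitude. Over the tabulated assumptions the contrast shifts by between −0.15 and +0.15 SD. With a common d, the shift is zero if switch rates are equal or if switchers and stayers do not differ.

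The stronger conclusion, that the plan flatters the lower amplitude on memory, is not supported: it presupposes both the switching pattern and a memory cost of the switch, and selection can offset or reverse the effect. Because the sign cannot be settled from the text, the comparison should be run and reported. It is a worthwhile improvement, not a flaw that invalidates the primary model.

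**What to change.** 1. Add an analysis of HVLT-R retention and the secondary cognitive measures at V2 and V3 by randomised amplitude. Use the same covariates and include all randomised subjects with available scores, switched subjects among them.
2. Report per arm the number switched and the number with V3 scores.
3. State the population, model and comparator of the bitemporal analysis, and whether randomised amplitude enters it.
4. Keep the on-assigned-settings model for the question about amplitude itself.
5. Base any statement that a lower amplitude spares memory over the series on both analyses.

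**Cost.** One further run of the existing cognitive model, a short table and a few lines of SAP text, with no change to treatment. V3 is scheduled for all subjects, so the scores should largely exist. However, seven subjects lacked the final assessment, and the text does not say whether switched subjects are among them; item 2 would show this.

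**Downside.** The as-randomised contrast mixes amplitude with the later switch. It answers a question about a treatment strategy and should be labelled as such.

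### Does naming only Tukey's method, with no stated family, alpha or gate, leave the amplitude contrasts on the two primary outcomes open to too many false findings?

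*Combined protocol and SAP*

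**What the plan says.** The Study Protocol section sets up three arms: "Subjects were randomized and blinded to 600, 700, and 800 mA prior to the first ECT treatment". The Statistical Analyses section introduces the main models with "For the primary outcomes (change in HDRS₂₄ and HVLT-R retention raw score", and gives each outcome its own longitudinal model. Both models include visit (called progress), amplitude and the interactions "progress/amplitude, progress/sex, and progress/pulse width". The HVLT-R model adds one covariate for premorbid functioning.

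The pairwise comparisons are then introduced by "Follow-up contrasts included the following". The second item in that list is "amplitude contrasts during the mid- and post-ECT assessments", illustrated by HDRS-24 "differences 600 and 700 mA at V2". The closing sentence says that the amplitude contrasts are averaged over sex and pulse width, and it names Tukey's "method for multiple pairwise comparisons".

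The section gives no significance level and does not say which set of means Tukey's method covers. It names neither visit as the main one. It does not say whether the contrasts depended on a significant progress/amplitude test, or how the two primary outcomes are to be judged together.

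**The concern.** Tukey's method controls error only within the family of means it is applied to. The illustration in the text is one pair at one visit, so a reader may suppose that the adjustment covers the three pairs at a single visit and is repeated for each visit and each outcome. That would make four separate families, each free to produce a false finding at its own 5%, with nothing linking them.

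At stake is the meaning of an adjusted p-value. These are the only comparisons between arms listed for the primary outcomes, so they would carry any statement that one amplitude differs from another. If the error rate over the set were near 19%, an isolated adjusted p-value just under 0.05 would be weaker evidence than it looks. Even for a reader who treats the two outcomes as separate questions, per-visit adjustment would leave 7–10% within one outcome over two visits.

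**Working it through.** The plan states no alpha, power or familywise rate, so there is no figure of its own to reproduce. The check asks how far the false-finding chance moves under each rule the text allows.

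**Inputs from the documents**
- Arms: 3 (600, 700, 800 mA), allocated 1:1:1, so 3 pairs.
- Visits at which arms are contrasted: 2 (V2, V3).
- Primary outcomes: 2.
- Subjects: 47 + 15 = 62, about 20 per arm.

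**Assumptions not in the documents**
- 5% two-sided for each Tukey family or overall test.
- Correlation between visits 0 to 0.9, and between outcomes 0 to 0.5.
- All arms truly equal.
- Covariates, imputation and completer selection ignored.

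**Count.** 3 pairs × 2 visits × 2 outcomes = 12 contrasts. Per-visit Tukey groups them into 2 × 2 = 4 families.

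**Independence value.** 1 − (1 − 0.05)^4 = 1 − 0.8145 = 18.5%. For one outcome over two visits: 1 − 0.95² = 9.75%.

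**Correlated case.** Three arm means were simulated at each visit and outcome. The largest pairwise difference, in standard-error units, was compared with the large-sample Tukey critical value. That value is 2.344 for three means, 2.850 for six and 3.10 for nine.

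| Rule (5% level assumed) | Chance of any false amplitude finding, both outcomes |
|---|---|
| Tukey per visit, no prior test | 18.5%, 17.4%, 16.1%, 12.9% at visit/outcome correlations 0/0, 0.5/0.1, 0.7/0.2, 0.9/0.5 |
| Joint adjustment of the six V2 and V3 contrasts, separately for each outcome | 9.2–9.8% |
| Tukey per visit, only after a 5% overall amplitude test on V2 and V3 in that outcome | 6.6–8.4% (visit correlation 0.3–0.8, outcome correlation 0–0.3) |
| Tukey per visit, only after a 5% progress/amplitude test (4 df, V1 included) | 1.1–5.5% |
| Tukey over six means (2 visits × 3 amplitudes) per outcome | 3.5–4.8% |
| Tukey over nine means (3 visits × 3 amplitudes) per outcome | 1.6–2.2% |

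The per-visit figure for one outcome alone is 7.1–9.7%. Small-sample versions of the first row give 13.0–18.6% (30–55 df) and 13.2–18.8% (20 per arm, 57 df), so sample size does not alter the picture. The two rows with a prior test hold only when all arms are equal at every visit; a real difference at one visit could open the gate for the other.

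**Cost of a stricter rule.** Joint adjustment within an outcome needs a large-sample critical value of 2.49–2.60. Adding Holm across the two outcomes makes the first step 2.74–2.84. Against 2.344:
- 2.49/2.344 = 1.06 and 2.60/2.344 = 1.11, a rise of 6–11%.
- 2.74/2.344 = 1.17 and 2.84/2.344 = 1.21, a rise of 17–21%.

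If six-mean or nine-mean Tukey was what the analysts used, joint adjustment within an outcome would instead lower the critical value, from 2.850 or 3.10 to 2.49–2.60. Joint adjustment plus Holm also leaves 6.6–6.7% error on single contrasts when one outcome truly differs. Only half alpha in each outcome brings that down, to 4.1–4.2%.

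**The case for a change.** The strongest case for a change is that the omission is certain. The contrast count is right, the arithmetic reproduces, and no wording in the section rules out per-visit Tukey with no prior test. The word follow-up hints at a preceding overall test but sets no rule, and two reasonable versions of such a test give different error rates (1.1–5.5% and 6.6–8.4%). Stating alpha, the family and any gate would take a few sentences, and a joint re-analysis would need no new data.

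Much of this stands. The text leaves the error rate of an adjusted amplitude difference undetermined, and within one outcome the per-visit reading would exceed 5% whatever view is taken of the two outcomes together.

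Three things do not carry over to a required change. First, the per-visit reading rests on an illustration that shows what one contrast looks like and says nothing about the family. A fitted model with three visits by three amplitudes supports the nine-mean family at least as well. Second, HDRS-24 and HVLT-R retention address efficacy and cognition, and the plan has no rule that success on either one counts as success for the trial, so pooled control is a matter of judgement. Third, replacing the adjustment without knowing which one was used could make it looser. It would also require the contrast covariance and degrees of freedom to be pooled over the multiple imputations, which is more work than re-reading fitted output.

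**Conclusion.** No change to the plan follows. Depending on the unwritten rule, the chance of any false amplitude finding on either primary outcome runs from about 1% to about 19%. The upper end requires 5% at each visit, no prior test and low correlations, none of which the documents state. Several permitted readings sit at about 5% or less, others at 7–10%, and the plan sets no familywise target that any of them would breach. No inflated error rate is established.

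What is missing is detail that the analysts must already have settled, since the section reports the analysis in the past tense and Tukey's method cannot be run without choosing a family. Publishing that choice would help a reader interpret the p-values, but it would not change the models, the contrasts or the analysis set. Going further, to joint adjustment with Holm across an efficacy and a cognition outcome, trades a 17–21% higher critical value in 62 subjects for a form of control the plan never claimed. That is a fair trade-off either way. Until the rule is known, a sensible reader gives little weight to a single adjusted amplitude difference that only just reaches significance. All percentages here depend on the assumed 5% levels and correlations and ignore covariates, imputation and the restriction to completers.
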